12.2. Analysis of negative sputum culture on solid media

LJ solid media will be performed at the following visits only: WK00, WK08, WK12, WK16, and FU1-FU4. The proportion of participants with culture negative timepoint at each visit will be calculated by treatment arm for each of the ITT and AA analysis populations. Participants will be classified as culture negative, culture positive, contaminated, culture result missing, participant died, or participant lost to follow-up (if lost to follow-up prior to that time point).

12.3. Development of drug resistance

Any changes in drug resistance profile from baseline will be listed including baseline and any follow-up drug resistance data, culture results, and treatment arm.

12.4. Analysis of Experimental Efficacy Endpoints

The molecular bacterial load assay (MBLA) and the sputum Lipoarabinomannan (LAM) assay will be evaluated against the conventional drug development endpoints, bacterial load measured in the BD MGITTM liquid media culture system. Comparisons between methods will be performed on a per-sample, per-patient, and per-treatment arm basis.

12.5. Handling of missing data

No missing data will be replaced, unless otherwise specified above, and will be shown in any summaries as missing.

12.5.1. Missing Dates

Imputation rules for missing or partial medication start/stop dates for concomitant medications and date of onset for AEs are defined below:

- 1) Missing or partial start date:
 - a) If only DAY is missing, use the first day of the month. UK(missing)-MMM-YYYY: impute to 01-MMM-YYYY;
 - b) If DAY and Month are both missing, use the first day of the year. UK-UKN-YYYY: impute to 01-JAN-YYYY;
 - c) If DAY, Month and Year are all missing, use the date of initial screening.
- 2) Missing or partial stop date:
 - a) If only DAY is missing, use the last day of the month.
 - b) If DAY and Month are both missing, use the last day of the year.
 - c) If DAY, Month and year are all missing, assign 'continuing' status to stop date.

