#### **10.5** Schedule of events

The trial consists of the following periods:

- Screening period: Visit SCR (Day -8 to 0)
- Experimental Treatment Period: Weekly visits from Visit WK00 (Day 01) to WK16 (Day 112 ± 2 days).
- Follow-up period: Visit WK18 (Day 126 ± 4 days), WK26 (Day 182 ± 7 days), WK38 (Day 266 ± 7 days), WK52 (Day 364 ± 7 days)

A tabular overview of the individual timing and details of the respective procedures and laboratory samples to be done at each visit can be found in the Schedule of Events, p.13.

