## 14.2 Clarifications and exceptions

Occurrences will be registered as AE from administration of the first dose of study drugs. All events that occur or are elicited before administering any study drugs, e.g. screening laboratory abnormalities qualifying as Adverse Events, will be recorded as medical history. If such events meet criteria for seriousness, they will nevertheless be reported as SAEs.

Abnormalities which are not clinically significant as per the qualified judgement of the investigator do not constitute adverse events and are not recorded and reported as such. However, these abnormalities may be analysed and reported in the study report.

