## 14.8 Adverse event reporting

Adverse events will be recorded by the investigator from the time a participant signs the informed consent form.

Any AE (serious or non-serious) observed by the investigator or reported by the subject will be recorded in the source data and on the Adverse Event electronic case report form (eCRF). The Investigator will review each AE and assess its relationship to the study treatment based on all available information at the time of the visit. The following information will be recorded for each AE reported:

- Diagnosis of the AE, if possible. In the case where an overall diagnosis cannot be made, each specific sign and/or symptom will be recorded as individual AEs; where possible the wording in the CTCAE should be used.
- Date of onset
- Stop date (duration) if applicable
- Severity (grade)
- Action taken with IMP/non-IMP study drugs
- Other action taken
- Outcome
- Relationship to IMP/non-IMP study drugs
- Occurrence
- Seriousness

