13.1.2. Adverse Events (AE)

The incidence of treatment-emergent adverse events, defined as all AEs that occur after the administration of IMP, and their relatedness to experimental treatment will be summarized by treatment group, by system organ class and preferred term, maximum severity, and potential relationship to IMP, SAE, as well as TEAEs with an outcome of death, serious TEAEs, and discontinuations due to TEAEs. These summary tables will be restricted to AEs with date of onset during or up to 14 days after treatment. Separate summary tables will be created for the incidence of AEs over the whole study period.

Adverse events will be coded by System Organ Class (SOC) and Preferred Term (PT) using the Medical Dictionary for Regulatory Activities (MedDRA) dictionary.

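### The SAP imputes adverse event onset to the earliest possible date with no floor at first dose, so some on-treatment events drop out of the treatment-emergent tables

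*SAP*

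**What the plan says.** The scope of the rule is explicit in SAP 12.5.1: "Imputation rules for missing or partial medication start/stop dates for concomitant medications and date of onset for AEs are defined below". Three start-date rules follow:

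- Day missing: "If only DAY is missing, use the first day of the month".
- Day and month missing: "If DAY and Month are both missing, use the first day of the year".
- Everything missing: "If DAY, Month and Year are all missing, use the date of initial screening".

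SAP 13.1.2 describes treatment-emergent AEs as "defined as all AEs that occur after the administration of IMP". It limits those tables to onsets during treatment or within 14 days after it, and adds separate tables for the whole study period.

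Protocol 10.5 places screening before treatment ("Visit SCR (Day -8 to 0" for screening, Day 01 for the first treatment visit).

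The protocol gives two starting points for AE collection. Section 14.2: "Occurrences will be registered as AE from administration of the first dose of study drugs", with earlier findings going to medical history. Section 14.8: "Adverse events will be recorded by the investigator from the time a participant signs the informed consent form".

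**The concern.** For medication, assuming the earliest possible start is harmless or cautious. For AE onset it can place an event before the exposure that may have caused it. Neither document sets a floor at first dose, and neither says that an event of unknown onset counts as treatment-emergent. Under Protocol 14.2 an AE record is post-dose by construction, yet the SAP would give it a pre-dose date. Section 14.8 blurs this by starting collection at consent, so the record alone does not settle the matter, and the two sections must be reconciled.

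At stake are the by-arm treatment-emergent tables. Safety is a primary objective, the trial is meant to guide dose choice, and with 15 participants per arm single events are visible.

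**Working it through.** The documents give no rate of missing AE dates, so there is no planned figure to reproduce. What can be checked is what each rule does to an event whose date is missing in that way.

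**Fully missing onset.** The imputed day lies between -8 and 0, and first dose is Day 1. The imputed day is below 1 in every case, so 100% of these events fail both the treatment-emergent definition and the onset filter.

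**Partial dates, true onset on treatment.** Let F be the first-dose date and O the true onset. An event is moved before first dose when the first day of O's month (day missing), or 1 January of O's year (day and month missing), is earlier than F. I counted every pair of first-dose date and onset day from 1 to 112. First doses were spread evenly over the planned recruitment period (Q3 2021 to Q1 2022, 274 dates) or, because actual enrolment dates are not given, over one calendar year (365 dates).

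| First doses | Pairs | Day missing | Day and month missing |
|---|---|---|---|
| Q3 2021 to Q1 2022 | 274 × 112 = 30,688 | 4,038 / 30,688 = 13.2% | 24,360 / 30,688 = 79.4% |
| One calendar year | 365 × 112 = 40,880 | 5,373 / 40,880 = 13.1% | 34,552 / 40,880 = 84.5% |

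Extending onset to day 126 (112 + 14) gives 11.7% for day missing, and 76.8% or 82.6% for day and month missing.

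**Partial dates, true onset after the window.** AEs are collected to week 52, so onsets on days 127 to 364 also exist. The same count asks how often the imputed date lands on days 1 to 126.

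| First doses | Pairs | Day missing | Day and month missing |
|---|---|---|---|
| Q3 2021 to Q1 2022 | 274 × 238 = 65,212 | 4,038 / 65,212 = 6.2% | 29,988 / 65,212 = 46.0% |
| One calendar year | 365 × 238 = 86,870 | 5,373 / 86,870 = 6.2% | 29,988 / 86,870 = 34.5% |

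For example, with first dose on 15 October 2021 and true onset on 2 May 2022 (day 200), losing day and month gives 1 January 2022, which is day 79 and counts as on treatment.

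**Effect on an arm.** One participant whose only qualifying event is removed: 1/15 = 6.7 percentage points.

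**With a floor at first dose.** For a true on-treatment event, both F and the first day of the known month or year are no later than O. The later of the two therefore lies between F and O, and the share moved before first dose is 0% under all three rules.

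**The case against.** The strongest reply is that very little will be affected. Protocol 14.8 requires an onset date for each AE, 14.4 has complaints elicited at every visit (weekly on treatment), 15.5 provides automatic completeness queries, and 16.3 requires queries to be resolved before lock. The percentages above are shares of events with a given kind of missing date, not of all AEs, and the count behind them may be near zero. Vague dates are more plausible in follow-up, where visits are 8 to 14 weeks apart and the error can run upward. All of this stands, and it limits the size of the problem.

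Three stronger readings are tempting and are not supported:

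- **That the rule can only lower treatment-emergent counts.** This is true for fully missing dates. For partial dates the second table shows movement in the other direction.
- **That the primary safety endpoint is undercounted.** SAP 5.1.1 refers to assessment during treatment and follow-up and does not apply the treatment-emergent filter. The endpoint is affected only if it is programmed from treatment-emergent records.
- **That events are lost from the report.** SAP 13.1.2 keeps them in the whole-study tables.

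The 6.7-point shift also needs the lost event to be the participant's only qualifying one. For overall incidence that will be rare: Protocol 7.4 reports at least one treatment-emergent event in 57 of 60 and 50 of 59 patients on related regimens. It matters more for individual terms.

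Finally, SAP 13.1.3 says that imputed dates decide classification for medication, and 13.1.2 has no such sentence for AEs. That they also drive the AE tables is an inference. It is the natural one, because the onset filter in 13.1.2 is where AE onset date decides table membership.

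**Conclusion.** The point holds as a specification error. A fully missing AE onset is always dated before first dose and always leaves the treatment-emergent tables. Partial dates do the same to about 13% (day missing) and 79 to 85% (day and month missing) of true on-treatment onsets, assuming uniform onset over 112 days and evenly spread first doses. For partial dates the net direction is not fixed, since about 6% and 35 to 46% respectively of onsets on days 127 to 364 (also taken as uniform) are pulled into the window. The number of events is unknown and probably small. The error should be corrected because the rule gives a wrong answer on its own terms and is cheap to change, not because a large distortion is expected.

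**What to change.** For AE onset only, amend SAP 12.5.1 as follows:

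- Day, or day and month, missing: use the later of the first-dose date and the first day of the known month or year.
- Onset fully missing: use the first-dose date.
- Exceptions to both: the known date parts or the stop date show that the event ended before first dose; or the known date parts, or the visit at which it was first reported, show that onset fell after the treatment-emergent window.

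Keep the current rule for concomitant medication. State in SAP 13.1.2 that imputed AE dates drive the treatment-emergent flag, and whether the primary safety endpoint uses that flag. Reconcile Protocol 14.2 with 14.8 on when AE collection starts.

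The cost is a few sentences and a small programming change. The downside is that a few pre-dose or follow-up events of unknown date may be counted as treatment-emergent. Flagging imputed onsets in the listings would let a reader see how many.

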12.6. Visit Windows

For timing of data items, the time is based on actual visit dates where data was collected (e.g. blood sample, sputum sample, data recorded) rather than scheduled visit name or date. The time from randomization is calculated as the difference between visit date and randomization date + 1 (so that data collected on the day of randomization is on day = 1).

Any visit, scheduled or unscheduled, that falls into the analysis window below will be assigned to that visit for the purpose of analysis. If two visits fall within the same interval, the one closet to the target date will be used for the analyses by visit, so that there is only one unique visit for each patient and analysis time-point. These visit windows relate to analyses of tabulations of data by visit.

Visit	Target Date: Days after Treatment	nt Analysis Window
	Allocation (wk*7+1)	
Baseline	1	Date of screening consent-3
Week 01	7	4-10
Week 02	14	11-17
Week 03	21	18-24
Week 04	28	25-31
Week 05	35	32-38
Week 06	42	39-45
Week 07	49	46-52
Week 08	56	53-59

Week 09	63	60-66
Week 10	70	67-73
Week 11	77	74-80
Week 12	84	81-87
Week 13	91	88-94
Week 14	98	95-101
Week 15	105	102-108
Week 16	112	109-121
Week 18	126	122-154
Week 26	182	155-210
Week 38	266	211-313
Week 52	364	314-no upper bound

13. Safety Analysis

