## 2 SCHEDULE OF EVENTS

Time points	Screening		Treatment						Follow-up													
			Treatment visit days each ± 2 days (except for WK2 visit, which may occur with a window of -2 days only						Follow-up visit 1 ± 4 days Follow-up visit 2 each ± 7 days		- 4 A											
	Day -8 to 0	Day 01	Day 07	Day 14	Day 21	Day 28	Day 35	Day 42	Day 49	Day 56	Day 63	Day 70	Day 77	Day 84	Day 91	Day 98	Day 105	Day 112	Day 126	Day 182	Day 266	Day 364
Visit	SCR	WК 00	WК 01	WK 02	WК 03	WK 04	WК 05	WK 06	WК 07	WК 08	WK 09	WK 10	WK 11	WК 12	WК 13	WK 14	WK 15	WК 16	FU 1 WK 18	FU 2 ^ WK 26	FU 3 ^ WK 38	FU 4 WK 52
Informed Consent	х																					
Check in-/exclusion criteria	х																					
Height	х																					
Demographics	х																					
Medical history	х																	1				Í
Serum pregnancy test B	x										XB							1	x B			
HIV test (+ CD4 count + viral load) c	х																					
Urine drug screening D	х																	1				
Chest X-ray	х																	1				
Enrolment & Randomization		х																				
Hospitalization				xĸ																		
Sputum E	1 x	3x	3x	Зx	3x	3x	Зx	3x	3x	Зx	Зx	3x	3x	Зx	3x	3x	3x	3x	2x	2x	2x	2x
2x per visit: MGIT, MBLA, (LJ culture, ZN smear), rest: storage E		x	x	x	x	x	x	x	x	x	x	х	x	x	x	x	х	x	x	x	x	x
Physical examination, vital signs F	х	XG	х	XG	х	х	х	х	х	х	х	х	х	х	х	х	х	х	x	(x G )	(x G )	(x G )
Neurological examination/vision testing G	х		x	x	x	x	x	x	x	x	x	x	x	x	x	x	х	x	x	(x)	(x)	(x)
ECG (12-lead; pre-dose) H	1x	3x	1x F	1xF	1x F	1x F	1x F	1x F	1x F	1x F	1x F		1xF		1xF			1xF				ĺ
Drug Susceptibility Testing	x	х														(x)						
Screening/Safety Lab J	X		х	X	х	х	х	х	х	х	х		х		х			х	x			
Study treatment A		х	х	х	х	х	х	х	х	х	х	х	х	х	х	х	х	х				
Intensive PK sampling K				х																		
Biomarker/PG blood sample L	х			х		х			х				х		х			х				
Concomitant Medication	х	х	х	х	х	х	х	х	х	х	х	х	х	х	х	х	х	х	x	x	х	Х
Adverse Events		х	х	х	х	х	х	х	х	х	х	х	х	х	х	х	х	х	x	х	х	Х

Key: WK: week of treatment; MGIT: liquid media (BD mycobacterium growth indicator tube; LJ: Loewenstein - Jensen solid media; MBLA: molecular bacterial load assay; PK: pharmacokinetics, X: refers to all visits mentioned above, ZN: Ziehl-Neelsen stain, PG: pharmacogenomics

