#### 9.2.2 Secondary Efficacy Endpoints

Further efficacy of DZD will be evaluated by assessment of:

- Proportion of patients who suffer relapse, defined as recurrent disease caused by a strain identical to the baseline isolate, within 12 months post randomisation, out of patients completing 16 weeks of therapy and achieving stable culture conversion to negative (SCC) as defined below by week 08, with no positives to follow by the week 16 visit.
- Time to recurrent TB, and to relapse, within 12 months post randomisation
- Time to stable sputum culture conversion (SCC) to negative on liquid media (defined as two negative cultures without an intervening positive culture). Time will be measured as time on treatment until the first negative culture.
- Proportion of participants who achieved SCC at each time point during treatment
- Proportion of participants with negative sputum culture on solid media at WK 08 and other timepoints
- Proportion of participants developing drug resistance among those not converting to negative culture

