# **10.4 Exclusion Criteria**

Participants for whom **one of the following** criteria is met will be excluded from trial:

- 1. Circumstances that raise doubt about free, unconstrained consent to study participation (e.g. prisoner or mentally handicapped person)
- 2. Poor general condition where delay in treatment cannot be tolerated or death within four months is likely.
- 3. Poor social condition which would make it unlikely that the patient would be able to complete follow-up
- 4. The patient is pregnant or breast-feeding.
- 5. The patient is infected with HIV with a CD4 count <220 cells/mm^3. If >220 cells/mm^3, patients will be included only if **any** of the following is applicable:
  - The patient is antiretroviral (ARV) naïve and able to postpone commencing HIV treatment for 2 months after the trial has started and then restrict regimens to those containing dolutegravir (see section 12.6.2 on ARVs)

or

The patient is ARV experienced (has been on ARV's a minimum of 5 months) and able to switch to a dolutegravir-based regimen.

- The patient is treated with nucleosidic reverse transcriptase inhibitors (are permitted as concomitant medication).
- The patient is treated with protease inhibitors as part of antiretroviral treatment regimens, which will be stopped at least 3 days before the start of study treatment (WK01, day1) for a patient to be eligible.

- The patient is treated with Efavirenz as part of antiretroviral treatment regimens which would have to be stopped 14 days before the start of study treatment (WK00, Day 01) for a patient to be eligible.
- 6. The patient has a known intolerance to any of the study drugs or concomitant disorders or conditions for which study drugs or standard TB treatment are contraindicated.
- 7. The patient has a history of, or current evidence of clinically relevant cardiovascular metabolic, gastrointestinal, neurological, psychiatric or endocrine diseases, malignancy, or any other condition that will influence treatment response, study adherence or survival in the judgement of the investigator, especially:
  - a. Neuropathy, or significant psychiatric disorder like depression or schizophrenia; especially if treatment for those has ever been required or is anticipated to be required
  - b. Clinically significant evidence of extra-pulmonary TB (e.g. miliary TB, TB meningitis, but not limited lymph node involvement)

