# 10.5.2 Treatment Period

Visits WK 00 – WK 16 (Day 01 – Day	11	2, each ±2 days with exception of day 14 (-2 days window))
Administrative & regulatory	•	Randomization (before/at WK00 only)

Protocol No: PanACEA - DECODE – 01/ LCB01-0371-20-2-02 Protocol Version No: V2.1, dated 08 September 2021

		
 
Enrolment (WK00 only)
 
Hospitalization* (WK 02 only)
 

Clinical (before intake o	of IMP)	
 
Physical examination, vital signs, weight Additional blood pressure and heart rate measurements at WK00: 1h, 2h and 3h (± 10 mins) after intake of IMP, at WK02 during hospitalization: 1h, 2h, 3h, 4h, 6h (± 10 ins) after intake of IMP with a meal
 
Neurological examination/vision testing (not WK 00)
 
Concomitant medication
 
Adverse events
 
Hospitalization: WK02 visit only, for intensive PK sampling after dosing together with standardized meal.
 

Laboratory Blo (before intake of IMP)	Blood	
 
Safety Lab (WK01-09, WK11, WK13, WK16): haematology and biochemistry (blood sample of 9.5mL), Coagulation only at WK 02 and if clinically indicated (additional blood sample of 3mL); to be sampled before study treatment administration
 
Serum pregnancy test (blood sample of 7.5mL), if female of childbearing potential (WK09 only)
 
Host biomarker blood sampling only at WK02, WK04, WK07, WK11, WK13 and WK16, if consent for this sub study is given
 
Intensive PK sampling DZD (WK02 only): 0 (within 1h before dosing), 1, 2, 4, 8, 12, (± 10 mins) and 24 hours (± 30 mins) after dosing
 

-	Urine	• Urinalysis (WK01-09, WK11, WK13, WK16): per dipstick, additional microscopy on abnormal dipstick results
Microbiology		
 
Sputum (3 samples per visit, one of which may be an early morning sample – to be specified in the microbiology laboratory manual)
 
AFB smear from screening and WK16 samples
 
Culture in BD MGIT liquid media from 2 spot sputum samples
 
Culture on LJ solid media from 2 samples (WK00, WK08, WK12 and WK16 only)
 
Susceptibility testing: minimum inhibitory concentration (MIC) for drugs the participant is receiving will be tested on a representative MTB isolate from baseline and from WK08 or later, if any growth detected
 
Storage of the 3rd sputum sample
 

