11.2. Relapse

An important secondary outcome is the proportion of participants who suffer relapse among those completing 16 weeks of therapy, achieve early culture conversion to negative in liquid media if there is a culture negative timepoint at two consecutive visits, the first of which is at or before week 08, without an intervening culture positive timepoint, and terminating therapy.

All participants will be classified as follows:

- Not achieved culture conversion to negative before or at week 8 after randomization (based on the analysis visit window).
 These participants will not end treatment at week 16 according to the protocol and therefore are not included in the relapse analysis.
- Relapse defined as having two consecutive culture positive timepoints without an intervening culture negative timepoint where the first occurs after Week 16 after randomization (based on the analysis visit window) and the recurrence strain of MTb is shown to be the same as that at baseline. If strain typing results are missing or inconclusive, a recurrence will be considered a relapse (rather than a reinfection).
- Reinfection defined as having two consecutive culture positive timepoints without an intervening culture negative timepoint where the first occurs after Week 16 after randomization (based on the analysis visit window) and the recurrence strain of MTb is shown to be different from that at baseline.
- Died at any point during the study
- Culture positive timepoint when last seen (not meeting criteria for other outcomes above)
- Culture negative timepoint when last seen (not meeting criteria for other outcomes above)

Outcomes will be tabulated by treatment arm among all in the ITT analysis population and among those in the AA analysis population.

A sensitivity analysis will be conducted repeating this relapse analysis using the second definition of time to culture conversion described below under the latter part of section 11.4.

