11.4. Time to culture conversion to negative on liquid media

Participants will be classified as having culture conversion to negative in liquid media if there are two consecutive culture negative timepoints without an intervening culture positive timepoint. Any other results will be ignored for the calculation of time to culture conversion. Culture timepoints will be classified as negative or positive according to the trial definition under 11.1.

Time will be taken from the date of randomization to the first occurrence of two consecutive negative culture timepoints.

Culture positive timepoints that occur after culture conversion has been achieved do not affect time to culture conversion.

This will be the primary definition of time to culture conversion. Primary analysis will be performed based on the primary definition. We will, in addition, perform two sensitivity analyses with alternative definitions of time to culture conversion:

- 1) The definition will be as above, with the exception that culture conversion can only be achieved if the two consecutive visits assessed as culture negative timepoints without an intervening culture positive timepoint are at least 28 days apart.
- 2) The definition will be as above, with the exception that culture conversion is only achieved provided no further culture positive timepoints occur after 'culture conversion', in the period up to and including the week 16 visits (a subsequent culture positive timepoint effectively 'cancels' out culture conversion).

12. Analysis Method

12.1. Analysis of time to culture conversion by dose group.

Descriptive summary statistics, such as mean/median of the time to culture conversion will be tabulated. Proportion of participants achieving culture conversion at each time point during treatment will be summarized using the Kaplan-Meier estimator with 95% confidence intervals.

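### The SAP counts visit windows, the week-8 relapse cut and time to conversion from randomisation; the protocol counts from first dose and allows a gap between the two

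*SAP*

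**What the plan says.** **SAP.** Section 12.6 makes the randomisation date day 1: "The time from randomization is calculated as the difference between visit date and randomization date + 1". Weeks 01 to 15 have windows of target ± 3 days, Baseline ends at day 3 and Week 08 is days 53-59. The section says that the windows serve by-visit tabulations. Section 11.2 nevertheless uses them to classify outcomes. Its first category is "Not achieved culture conversion to negative before or at week 8 after randomization (based on the analysis visit window", and participants in it are kept out of the relapse analysis. Section 11.4 adds: "Time will be taken from the date of randomization to the first occurrence of two consecutive negative culture timepoints".

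**Protocol.** Section 9.2.2 defines the conversion endpoint differently: "Time will be measured as time on treatment until the first negative culture". Section 10.4 identifies Day 01 with first dose: "start of study treatment (WK00, Day 01". The treatment-period table in Section 10.5.2 lists "Randomization (before/at WK00 only", so randomisation may come before the first-dose visit. Section 13.5 requires complete screening results and proven eligibility beforehand but sets no maximum interval to first dose. The screening period in Section 10.5 is "Visit SCR (Day -8 to 0". The schedule in Section 2 puts enrolment and randomisation in the Day 01 column and gives the visit tolerance as "Treatment visit days each ± 2 days (except for WK2 visit, which may occur with a window of -2 days only".

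**The concern.** The two documents run on different clocks. Whenever randomisation precedes first dose, every SAP day is later than the protocol day by the length of the gap, and the SAP does not say how this is handled.

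This matters most at week 8. The protocol's decision to stop after 16 weeks depends on a first negative culture at or before the WK08 visit. The SAP decides membership of the relapse analysis by a window counted from randomisation. A participant can pass the first test and fail the second, and so be missing from the relapse analysis although their therapy was stopped. Separately, pre-dose data could be tabulated as on-treatment Week 01 data, and time to conversion would include days before treatment.

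**Working it through.** **The plan's own figure.** Week 08 target 56 ± 3 gives 53-59, as printed. The header formula wk*7+1 gives 8*7+1 = 57 for Week 08, while the listed target is 56. The listed targets follow wk*7 (7, 14, and so on), so header and table disagree.

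**Inputs.**
- g = days from randomisation to first dose. The documents do not give it. Day -8 to Day 01 sets an outer limit of 9 days.
- v = visit deviation, -2 to +2 days (Protocol Section 2; WK02 allows early visits only).
- Protocol days: WK00 = 1, WK01 = 7, WK08 = 56, WK16 = 112.
- SAP windows: Baseline to day 3, Week 01 = 4-10, Week 02 = 11-17, Week 08 = 53-59, Week 09 = 60-66, Week 16 = 109-121.

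**Formula.** SAP day = visit date - randomisation date + 1. Since first dose is g days after randomisation, SAP day = protocol day + v + g.

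| g | WK00 pre-dose | WK08 on time | WK08 1 day late | WK08 2 days late |
|---|---|---|---|---|
| 0 | 1, Baseline | 56, Week 08 | 57, Week 08 | 58, Week 08 |
| 1 | 2, Baseline | 57, Week 08 | 58, Week 08 | 59, Week 08 |
| 2 | 3, Baseline | 58, Week 08 | 59, Week 08 | 60, **Week 09** |
| 3 | 4, **Week 01** | 59, Week 08 | 60, **Week 09** | 61, **Week 09** |
| 4 | 5, **Week 01** | 60, **Week 09** | 61, **Week 09** | 62, **Week 09** |

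**Reading the results.**
- WK08 leaves its window when v + g is 4 or more. From g = 6, even a visit 2 days early is past it: 54 + 6 = 60.
- WK00 leaves Baseline when 1 + g exceeds 3, that is, from g = 3.
- At g = 3, WK00 (day 4) and an on-time WK01 (7 + 3 = day 10) are both 3 days from target 7. The SAP keeps the visit nearest the target and has no rule for ties.
- At g = 4, WK00 (day 5) is labelled Week 01, and the on-time WK01 (day 11) becomes Week 02.
- WK16 keeps its label up to g = 7, even when 2 days late: 112 + 2 + 7 = 121.
- Only a first negative at WK08 is realistically exposed. An on-time WK07 stays inside the cut even at the outer limit: 49 + 9 = 58.
- Time to conversion is longer by exactly g days.

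**After the change.** Counting from first dose is the case g = 0. WK00 is day 1, and every permitted WK08 visit falls on days 54-58, inside 53-59. Nothing is relabelled.

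**The case against.** The strongest reply is that the SAP assumes randomisation and first dose on the same day. The schedule table shows this, and the SAP targets for the weekly visits equal the protocol's treatment days. The words in Section 10.5.2 may mean no more than the day before, and the windows absorb one day on top of the visit tolerance. Affected participants would still be counted in SAP Table 2.10 as not converted. Randomisation is also a conventional origin for an ITT comparison, and the protocol itself uses it for the 12-month relapse horizon.

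Much of this stands. The harm depends on a gap that the documents permit but do not show, and the origin for the between-arm Cox comparison is partly a convention. Two things are not answered: the scope sentence in SAP 12.6 does not protect the relapse classification, because 11.2 calls on the windows by name; and the SAP gives no reason for leaving the protocol's time-on-treatment definition.

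A reader might go further in several ways that the documents do not support:
- **A general percentage of misassigned weekly visits.** That needs distributions of gaps and visit dates, which are not given. Nor do all weeks behave alike: WK02 allows early visits only, and Week 16 has a wider window.
- **An empty baseline culture.** The schedule lists MGIT culture from WK00, but Protocol 13.2 mentions culture at screening and SAP 12.1 adjusts for TTP at screening and enrolment.
- **Loss of the patients at highest relapse risk, or differences between sites.** Nothing in the documents gives relapse risk by conversion week or gaps by site.
- **Damage to the primary analysis.** The TTP model takes its data handling from SAP Section 8, which uses actual dosing and sampling times, and SAP 10.1 works on time on treatment.

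**Conclusion.** The conflict over the time origin is in the text and holds whatever the gap; so does the header error. Relabelling is conditional: none at gaps of 0-1 day. A WK08 culture moves to Week 09 at a gap of 4 days if on time, 3 if one day late and 2 if two days late. The pre-dose WK00 visit moves to Week 01 at 3 days or more. These thresholds assume only the printed windows and the permitted visit tolerance. How many participants are affected cannot be stated without the actual gaps.

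The reach is limited to the by-visit tables, relapse-analysis membership for participants first negative at WK08, and a shift of g days in a secondary time-to-event endpoint. That makes it a correction that should be made, not a threat to the primary efficacy result.

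**What to change.** 1. In SAP 12.6, set day 1 to the date of first dose of any study drug (Arm 1 receives no DZD). Apply this to the visit windows and to the week-8 cut in 11.2. Assign the last pre-dose assessment to Baseline.
2. In SAP 11.4, measure time to conversion from first dose, to match the protocol. If randomisation is kept as origin for the arm comparison, report the gap by arm and add a sensitivity analysis from first dose.
3. Keep randomisation as origin for the 12-month relapse horizon.
4. Correct the window-table header so that it agrees with the listed targets.

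The cost is SAP wording and, at most, one sensitivity analysis. The ITT population requires at least one dose, so every member has a first-dose date. Labels do not change for anyone dosed on the day of randomisation.
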